
inpatient non-steroidal anti-inflammatory drug (NSAID) use, amount of inpatient opioid use, incidence and severity of opioid systemic side effects, incidence and severity of local anesthetic side effects, catheter related issues, breast feeding success, maternal satisfaction, evaluation of wound healing, categorization and quantification of outpatient pain medication, and cost analysis.

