# **Objectives:**

The primary outcome measured in this study is post-operative pain with movement measured both during cough and 20° straight leg raise. Pain at rest will also be evaluated. All types of pain will be measured using a visual analogue pain scale (VAPS) determined using a 100mm line with the patient making a mark on the line between no pain and worst pain ever (12). Pain scores will be collected after the bolus of study medication/placebo (zero time), at PACU discharge (2hr), 6hr, 12hr, 24hr, 48hr, and 72hr post-cesarean section. Pain at 4-6 weeks and 3mo will be quantitated over the telephone using a numerical pain scale (NPS) with 0 being no pain and 10 being the worst pain imaginable. In addition to the pain scores, pain with movement will be further evaluated qualitatively using the short-form McGill pain questionnaire (22) at all time-points in the study. This will allow us to look at pain quality (sharp, burning, etc.), as well as examining the affective components (exhausting, fearful, etc.) of the pain.

There are several secondary outcomes of this study that can be divided into rescue medication information, medication side effects, breastfeeding, wound evaluation, patient satisfaction, and cost-analysis.

Rescue medication data will be collected during the hospitalization period (0-72hr). We will note the time to dosing with the first rescue medication for breakthrough pain. After the first rescue medication is given, the patients will be eligible for further doses of IV or

PO pain medicines for continued breakthrough pain as needed (see **Study Design and Methods** section below for specifics). The time to first opioid use for pain will also be recorded whether this entails IV or PO administration. Additionally, we will quantitate narcotic use in terms of morphine equivalents given (in mg) both by post-operative day and with a cumulative total. The total dose of NSAIDs (in mg) will be recorded for each of the first three postoperative days, along with a cumulative total. We will also be measuring the proportion of patients who require opioid supplementation at 0, 2, 6, 12, 24, 48, and 72 hours post-op. We will also ask if patients are still requiring opioids and/or NSAIDs for surgical discomfort along with inquiring about the amount of each used per day at the 4-6 week and 3 month follow-up telephone calls.

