
Ketorolac (30 mg IV) will always be given at the first request for additional pain medicine after leaving the operating room. Thereafter, the study patients will receive 30mg ketorolac q6hr prn pain for 24hr if their pain score is > 3. If their pain score remains > 3 twenty minutes after ketorolac administration, they can receive morphine 1mg IV q1hr until their pain score is  $\leq$  3. After 24hr, and through discharge, the study patients will receive1-2 tablets PO oxycodone-acetaminophen (5/325) q6hr for postoperative pain for pain scores > 3. Additional breakthrough pain still present 30 min after oxycodone-acetaminophen dosing will be treated with ibuprofen 600 mg PO q6hr. Again, if the pain score remains > 3 thirty min after ibuprofen dosing, IV morphine (1-2 mg q1hr) will be administered until the pain score is  $\leq$  3.

Each patient that ends up participating in our study will have a folder (see attached Data Collection Instrument) associated with her name. This folder will include all of the VAPS scoring sheets and the McGill pain scoring sheets obtained at the different time periods. It will also contain summary sheets for data abstracted from the medical, nursing, and pharmacy records such as uterine closure, LATCH scores, time to first rescue medication, time to first opioid use, and total opioid and NSAID use, etc. These folders will be stored in locked file cabinets in the main office of the EUHM Department of Anesthesiology where other sensitive patient information is kept securely. Data, without personal identifiers will be entered into Excel spread sheets and kept on the Emory Healthcare virtual desktop for further analysis.

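### The cumulative NSAID total adds ketorolac and ibuprofen in raw milligrams, so wherever ibuprofen is used it says almost nothing about ketorolac

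*Combined protocol and SAP*

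**What the plan says.** The Abstract lists among the secondary outcomes the amount of "inpatient non-steroidal anti-inflammatory drug (NSAID) use, amount of inpatient opioid use". The Objectives section defines the NSAID part: "The total dose of NSAIDs (in mg) will be recorded for each of the first three postoperative days, along with a cumulative total". The sentence before it treats opioids differently: "we will quantitate narcotic use in terms of morphine equivalents given (in mg) both by post-operative day and with a cumulative total".

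Study Design and Methodology supplies two NSAIDs for breakthrough pain:

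- Ketorolac: "Ketorolac (30 mg IV) will always be given at the first request for additional pain medicine after leaving the operating room", after which "the study patients will receive 30mg ketorolac q6hr prn pain for 24hr", subject to a pain-score threshold.
- Ibuprofen, in the regimen that starts after 24 hours: pain persisting after oxycodone-acetaminophen "will be treated with ibuprofen 600 mg PO q6hr".

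The summary sheets described in the same section again carry a total: "time to first opioid use, and total opioid and NSAID use, etc". The document gives no NSAID conversion factor, dose count or total by drug, and does not say whether a postoperative day is a 24-hour window or a calendar day.

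**The concern.** Milligrams of two drugs given at very different doses are not a common scale of analgesic use. The plan recognises this for opioids and leaves NSAIDs as a raw sum. The drug with the larger milligram dose then decides the total, whatever happens to the other.

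Ketorolac is the first rescue drug after the operating room and the only NSAID in the regimen for the first 24 hours. If ropivacaine reduces ketorolac use, that reduction does enter the cumulative total, but a handful of ibuprofen doses can hide or reverse it. The trial could then report no NSAID sparing although ketorolac use fell. Patient Safety and Potential Benefits names less use of opioids and other adjunctive pain medicines as an expected benefit, so this is a result readers will look for.

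**Working it through.** **Inputs from the document.** Ketorolac 30 mg per dose, every 6 hours as needed for 24 hours; ibuprofen 600 mg per dose (Study Design and Methodology). Twenty women per arm and a 0.05 significance level (Statistical Analysis). The plan has no design figure for NSAID use to reproduce. Its 20 per arm was set on pain scores, and nothing below depends on how it was derived.

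**Dose arithmetic (no assumptions about usage).**

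- Weight of one ibuprofen dose: 600 / 30 = 20 ketorolac doses.
- Four ketorolac doses in 24 hours: 4 × 30 = 120 mg, and 120 / 600 = 20% of one ibuprofen dose. If a fifth dose falls at hour 24: 150 mg, or 25%.
- Largest ketorolac share of a woman's total with one ibuprofen dose: 120 / 720 = 17%, or 150 / 750 = 20%. With eight ibuprofen doses (every 6 hours over 48 hours): 120 / 4,920 = 2.4%.
- Arm of 20, one fewer ketorolac dose each: 20 × 30 = 600 mg, equal to one ibuprofen dose in one woman. Two fewer each: 20 × 60 = 1,200 mg, equal to two ibuprofen doses in the whole arm.

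**Illustration (usage rates are assumptions).** Ketorolac doses follow Binomial(4, 0.75) in one arm and Binomial(4, 0.50) in the other, so means of 3 and 2 doses and a difference of 30 mg. Each woman takes one 600 mg ibuprofen dose with probability p, the same in both arms. The test is two-sided at 0.05, with no Bonferroni adjustment.

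Standard deviations show the mechanism. For ketorolac they are 30 × √(4 × 0.75 × 0.25) = 26 mg and 30 × √(4 × 0.5 × 0.5) = 30 mg. For ibuprofen the value is 600 × √(p(1 − p)): 131, 180, 260 and 300 mg at p = 5%, 10%, 25% and 50%. The 30 mg difference is unchanged while the noise around it grows several-fold.

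Simulated power (20,000 trials, 20 per arm):

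| Outcome analysed | t-test | Mann-Whitney |
|---|---|---|
| Ketorolac mg alone | 90% | 89% |
| Summed mg, p = 5% | 24% | 80% |
| Summed mg, p = 10% | 11% | 70% |
| Summed mg, p = 25% | 7% | 45% |
| Summed mg, p = 50% | 6% | 31% |

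A second simulation let each ibuprofen user take one or more doses, from eight opportunities each taken with probability 25%. With 10%, 25% and 50% of women using ibuprofen, t-test power on the summed total was about 5% throughout, and Mann-Whitney power was 67%, 39% and 15%.

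**The case against.** Four points can be made for the plan.

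1. **The same sentence also gives daily totals.** Ketorolac belongs to the first 24 hours and ibuprofen to the time after it, so a day-1 total over a 24-hour window would be essentially ketorolac. The 24, 48 and 72-hour assessments make that a natural reading. This is the strongest point, and it limits the concern to the cumulative total. It is not complete protection: the window is not defined, calendar days would mix the drugs, and the first-request ketorolac dose has no stated time limit, so it can fall in a day that also holds ibuprofen.

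2. **Equal ibuprofen use is one scenario.** The infusion may run up to 72 hours, so ibuprofen use could fall too. With eight ibuprofen opportunities per woman and use per opportunity falling by a third, t-test power on the summed total is about 95% (60% to 40%), 57% (30% to 20%) and 32% (15% to 10%). So the loss of power is not inevitable. But the signal is then ibuprofen. The mean ibuprofen differences are 8 × 0.20 × 600 = 960 mg, 8 × 0.10 × 600 = 480 mg and 8 × 0.05 × 600 = 240 mg, so the 30 mg from ketorolac is 30 / 990 = 3%, 30 / 510 = 6% and 30 / 270 = 11% of the total difference.

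3. **The t-test is the worst case.** The plan checks normality and turns to a rank method for non-normal data, and such a mixture is plainly non-normal. The rank figures are indeed milder, but still fall by about half at 25% uptake. The rank method named is the Friedman test, which is not a comparison of independent arms.

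4. **The data collection instrument is not in the available text** and may record each drug separately. If so, the data exist; the outcome as defined remains a sum.

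**Conclusion.** The concern holds for the cumulative NSAID total. The 20-to-1 weighting follows directly from the stated doses. How much it matters in practice depends on ibuprofen uptake and on whether that uptake differs between arms; the document gives neither. The power figures therefore illustrate the mechanism and do not predict the result. Under equal ibuprofen use, a ketorolac difference detectable with 90% power is largely lost to a comparison of means once 5-10% of women take a single ibuprofen dose, and partly lost to a rank test. If ibuprofen use falls as well, the total detects mainly that.

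The outcome is secondary, no test or power statement is attached to it, and no data are lost. It should be corrected because a named outcome, followed as written, does not measure what its label says.

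**What to change.** Replace the NSAID sentence in Objectives with, for example: *Ketorolac (mg) and ibuprofen (mg) will be recorded and analysed separately, by postoperative day (24-hour windows from zero time, the study bolus) and cumulatively over 0-72 hours.* Carry the same split into the summary-sheet item in Study Design and Methodology, and drop the summed-milligram total. If a single combined measure is wanted, prespecify it as a dose count or a cited conversion, and state its weighting as an assumption.

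No new data are needed: drug and dose come from the pharmacy and nursing records already being abstracted. The cost is two NSAID figures in place of one and one more secondary comparison. No dose or rescue rule changes.

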### **IRB** Protocol

### Multimodal Post-Cesarean Analgesia with Spinal Morphine and Continuous Wound Infiltration of Ropivacaine Using the OnQ® Elastomeric Pump: A Dose-Ranging Study Using a High-Volume, Low-Dose Protocol PI: [name]

Abstract:

The purpose of the proposed study is aimed to determine whether continuous subfascial infusion of ropivacaine using the On-O® elastomeric pump in combination with intrathecal (IT) preservative-free morphine (PFM) will improve post-operative cesarean section pain relative to IT PFM alone (the current standard of care). Using a doubleblinded, randomized, placebo-controlled study design, 60 women undergoing their first, second or third cesarean section will be randomly assigned to one of 3 different groups receiving either saline (control, n=20) or ropivacaine (0.1% or 0.2%, experimental groups n=20 in each) subfascially via the elastomeric pump. We will enroll up to 70 subjects to achieve 60 randomized and treated subjects, to account for screen failures and/or early terminations, All participants will receive an IT dose of 200mcg of PFM as part of a standardized spinal anesthetic for their operative procedure. During closure of their abdomen, all patients will undergo placement of a multi-orifice, silver-impregnated catheter in the subfascial space. At the conclusion of the surgery, the catheter will be bolused with 8ml of one of the three test solutions, after which an On-O® elastomeric pump (containing the same solution as initially administered through the catheter) will be attached to infuse the test solution at a rate of 8ml/hr. The infusion system will then be left in place for up to 72hr. Adjunctive pain medicines (ketorolac, morphine, ibuprofen, and oxycodone-acetaminophen) will be available for the treatment of breakthrough pain during hospitalization. The primary outcome being measured in the study is postoperative pain with movement as assessed immediately after the study bolus (baseline) and during the immediate post-operative period, when leaving the PACU (2hr), 6hr, 12hr, 24hr, 48hr, and 72hr post-op. Pain will also be evaluated by telephone at 4-6 weeks and 3mo after surgery. A visual acuity pain scale (VAPS) will be used to measure patient pain levels while hospitalized whereas pain at the 4-6 week visit and 3mo will be quantitated using a numeric pain scale (NPS). Secondary outcomes to be studied include degree of pain at rest, time to first rescue medication, time to first opioid use, amount of

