As several different medications are utilized within this study, it is important to monitor side effects of the medications, and see if these profiles change under the conditions of the study. We will collect data on the incidence and severity of opioid central and/or systemic side effects – pruritus, nausea/vomiting (not associated with hypotension), somnolence, and respiratory depression. Somnolence will be graded using a published perioperative somnolence scale (23). Measurements of nausea/vomiting and pruritus will make use of previously published scales (24). Respiratory depression will be considered to be present if the respiratory rate is < 10 breaths/min. We will also make note of both the type and amount of treatment given for these opioid-related side-effects. In addition, we will collect data on the incidence and severity of ropivacaine systemic side effects – tinnitus, perioral numbness, metallic taste, and seizures – and will characterize both the type and amount of treatment required.

Breast-feeding success and safety will be monitored during this study. Breast feeding success will be measured using LATCH Scores (25) obtained in the PACU, and once per shift on the mother-baby unit for 72 hours. These will be assigned by either the labor and delivery nurses or by the nurses in the post-partum ward. We will also assess the proportion of mothers breast-feeding their infants at 24, 48, 72hr, and during their 4-6 week and 3 month follow-up phone calls. Maternal plasma and breast milk concentrations have been measured during epidural analgesia with ropivacaine (0.125%)

for labor, with the breast milk-plasma ratio being somewhere between 0.23 and 0.25 at 18-24hr (26). Surprisingly, the literature is silent regarding the concentration of ropivacaine in human breast milk after continuous wound infusion.

Both the cesarean section incision and the catheter insertion site will be evaluated. Any catheter- or infiltrate-related issues like wound infection and seroma formation will be noted. Wounds will be assessed for infection or dehiscence at 24, 48, and 72hr. At the 4-6 week and 3-month follow-up phone calls the patient will be asked about the presence of wound dysesthesia (numbness, tingling, burning, pricking, allodynia, or hyperesthesia). The patient will also be asked about the occurrence of infection, dehiscence, and keloid formation at this time.

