stattrek.com), and is on file at the research pharmacy. The code is not known by any of the investigators. The arms are as follows: 1) a bolus dose of 8ml of normal saline followed by an infusion of 8ml/hr of normal saline using an On-Q® elastomeric pump, 2) a bolus dose of 8ml of 0.1% ropivacaine followed by an infusion of 8ml/hr of 0.1% ropivacaine using an On-Q® elastomeric pump, or 3) a bolus dose of 8ml of 0.2% ropivacaine followed by an infusion 8 ml/hr of 0.2% ropivacaine using an  $On-Q^{\mathbb{R}}$ elastomeric pump. The pump will be filled to its maximum capacity of 550 ml and will infuse until the total volume is delivered. The patients will undergo their cesarean sections in the usual fashion through uterine closure. The peritoneum may or may not be closed and the rectus abdominis muscles may or may not be approximated as per the usual practice of the attending obstetrician. The obstetrician will insert a 20G guide needle/introducer assembly through the skin, subcutaneous tissue and rectus fascia about 3cm above and just lateral to the incision. When the introducer is fixed in the desired location, the guide needle is removed, and a multiport, silver-impregnated catheter (6-10cm) is placed above the rectus muscle parallel to the fascial incision. The fascia is then closed above the rectus muscles, and the rest of the closure occurs as per the usual practice of the surgeon. After closure is complete, one to two drops of a topical skin adhesive (2-octvl cvanoacrylate or SurgiSeal®) will be placed on the skin at the exit site of the multiport catheter and the catheter will be further secured with adhesive surgical strips. The exit site, along with a small length of catheter will then be covered with a sterile bio-occlusive dressing. The hospital pharmacy will have delivered a 10 ml syringe filled to 8ml with the bolus test solution, along with an On-Q® elastomeric pump loaded with the same solution to the operating room prior to, or during, the cesarean section. The test solutions are all water-white in color, and will have no discerning markings to indicate whether it is saline or one of the two concentrations of ropivacaine. The preparing pharmacist will be the only person not blinded to the study. At the termination of the surgical procedure, the obstetrician will administer the 8ml bolus of test solution via the catheter using the 10ml preloaded syringe, followed by attaching and activating the elastomeric pump which will be pre-set to deliver 8ml/hr of test solution.

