# **Statistical Analysis**

Based on a preliminary sample size calculation using an  $\alpha$  risk of 0.05, a  $\beta$  risk of 0.2, and an effect size involving a 40% reduction in pain scores, we estimate that 20 patients are needed in each arm of the study. Data normality will be tested using the Kolmorgorov-Smirnov test. Normally distributed data will be presented as means  $\pm$  SD, whereas non-normally distributed data will be expressed as medians with interquartile ranges. Categorical data will be reported as frequencies. VAS scores will be analyzed using two-way ANOVA for repeated measures. Non-normal data will be analyzed using the Friedman test. Categorical data will be analyzed using the X test. Multiple comparisons will use a Bonferroni correction. Differences will be considered statistically significant at a P<0.05.

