Additionally, patients in the study will be immediately unblinded via phone call to the pharmacy in the three following situations: a) if they experience any 2 of 4 minor LA toxicities (perioral numbness, metallic taste in mouth, tinnitus, or light-headedness); b) any signs of severe systemic toxicity (seizures, arrhythmia, obtundation, cardiac arrest); or allergic reactions which appear by timing as due to LA administration (hives, angioedema, anaphylaxis). Minor toxicities will be treated by simply stopping the infusion and watching the patient for 6hr (approximately 3 half-times in circulation - product insert). Major toxicities will be treated by stopping the infusions and providing

appropriate supportive or resuscitative care. It is felt that major toxicity is very unlikely considering the drug utilized, the drug dosage, the use of a clinically-approved delivery device, and the restrictions on recruiting patients with LA allergies.

The OnQ® elastomeric pump and silver-impregnated catheter are FDA-approved devices for the treatment of post-surgical pain after all types of surgery including cesarean section. Theoretically, it could be argued that there is a small risk of skin or wound infection due to the presence of a tunneled percutaneous catheter for three days. This risk will be mitigated in three ways. First, sterile technique will be used throughout the procedure and the patients will be given antibiotic prophylaxis before the cesarean section. Second, the silver-impregnated catheter has inherent antimicrobial properties which prevent formation of a bacterial microfilm with subsequent catheter colonization; and also elutes silver directly into the implantation site where it may have direct antimicrobial activity (31). Finally, LAs themselves have intrinsic bacteriostatic and/or bactericidal properties against a wide range of pathogenic bacteria, and thereby continuous wound infusion with these agents might create an unfavorable milieu for infection (32).

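### The list of ropivacaine side effects to collect omits light-headedness, one of the four minor toxicities in the protocol's own unblinding rule, so isolated cases may go uncounted

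*Combined protocol and SAP*

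**What the plan says.** The Abstract includes "incidence and severity of local anesthetic side effects" among the secondary outcomes without naming any. The Objectives section does name them: the ropivacaine systemic effects to be recorded, with incidence, severity and treatment, are "tinnitus, perioral numbness, metallic taste, and seizures". No wording in that sentence marks the items as examples.

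Patient Safety and Potential Benefits sets out when a patient is unblinded. One trigger is "any 2 of 4 minor LA toxicities (perioral numbness, metallic taste in mouth, tinnitus, or light-headedness". Its consequence is also stated: "Minor toxicities will be treated by simply stopping the infusion and watching the patient for 6hr".

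Three other statements bear on the point:

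- **Arms.** The comparison is "saline (control, n=20) or ropivacaine (0.1% or 0.2%, experimental groups n=20 in each".
- **Blinding.** Study Design and Methodology says "The preparing pharmacist will be the only person not blinded to the study", so ward staff apply the rule without knowing the arm.
- **Data sources.** The same section refers to an attached Data Collection Instrument and says each patient's folder will hold "summary sheets for data abstracted from the medical, nursing, and pharmacy records".

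**The concern.** The protocol itself classes light-headedness as a sign of local anesthetic toxicity, serious enough to count toward breaking the blind and stopping the infusion. Its definition of the side-effect outcome leaves that symptom out.

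If the Objectives list is followed as written, two things happen. Isolated light-headedness is not counted at all. And a woman unblinded for light-headedness plus one other symptom shows only one listed symptom, so the side-effect data do not explain why her infusion was stopped.

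This is a dose-ranging trial with saline, 0.1% and 0.2% arms, and the Objectives section says it wants to see whether side-effect profiles change under study conditions. The saline arm could show how much light-headedness is background after cesarean section, but only if the symptom is recorded in every arm. A mild symptom that nobody wrote down cannot be reliably recovered later.

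**Working it through.** The plan gives no figure to reproduce on this point. The check is a comparison of two lists, followed by simple arithmetic on scale.

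**1. The lists side by side**

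| Symptom | Collection list (Objectives) | Minor toxicity in unblinding rule (Patient Safety and Potential Benefits) |
|---|---|---|
| Perioral numbness | yes | yes |
| Metallic taste | yes | yes |
| Tinnitus | yes | yes |
| Light-headedness | **no** | yes |

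Three of four minor symptoms match. Seizures, the remaining item on the collection list, belong to the rule's severe category.

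**2. Is it picked up elsewhere?** The opioid effects in Objectives are pruritus, nausea/vomiting, somnolence and respiratory depression; light-headedness is not among them. The supplied text has no general adverse-event collection section. The symptom appears only in the unblinding rule.

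**3. How far the rule depends on it.** Any two of four symptoms trigger unblinding: C(4,2) = 6 possible pairs. Pairs that include light-headedness: 3. A woman with light-headedness alone has one of four symptoms, so she neither triggers the rule nor appears on the collection list.

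**4. How many women.** The documents give no rate, so the rates below are assumed. Expected number with isolated light-headedness = n × rate, with n = 20 per arm and 60 in total (Abstract):

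| Assumed rate | Per arm (20 × rate) | All arms (60 × rate) |
|---|---|---|
| 2% | 0.4 | 1.2 |
| 5% | 1 | 3 |
| 10% | 2 | 6 |
| 20% | 4 | 12 |

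These women would be missed only if the form lacks the item and no abstracted record captures it.

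**5. What the recorded data could show.** The exact (Clopper-Pearson) two-sided 95% upper limit after zero events is 1 − 0.025^(1/n).

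- One arm, n = 20: 1 − 0.025^(1/20) = 0.168, or 16.8%.
- Both ropivacaine arms, n = 40: 1 − 0.025^(1/40) = 0.088, or 8.8%.

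These limits hold for any symptom at these sample sizes. They do not measure the omission; they show that any comparison between arms can only be descriptive.

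**The case against.** The strongest reply is that what gets recorded is set by the Data Collection Instrument, which is an attachment not in the supplied text. It may already carry light-headedness. That stands, and it is why the omission may lead to uncounted cases rather than certainly does. It does not remove the mismatch: the outcome as defined in Objectives would still differ from the protocol's own toxicity list.

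A second reply is that the lists do different jobs. A bedside trigger can reasonably be broader than an outcome definition, and light-headedness is the least specific of the four symptoms in women who have had abdominal surgery, a spinal anesthetic and opioids. The non-specificity is real, although the protocol does not give it as a reason for the omission. It argues for recording the symptom in all blinded arms so that saline shows the background, while accepting that 20 women per arm cannot firmly separate background from a drug effect.

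Third, a woman who is unblinded leaves a trail. Her other minor symptom is on the collection list, the infusion is stopped, and the pharmacy is telephoned. This largely stands: she would be counted as a case, though with one symptom instead of two. The main exposure is therefore isolated light-headedness.

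Fourth, arrhythmia, obtundation, cardiac arrest and allergic reactions are also in the rule and missing from the list. Those events prompt immediate unblinding and are likely to reach the abstracted records, so they are not part of this point. Staff must watch for light-headedness too, and nursing notes are abstracted, but capture of a mild, isolated symptom by that route is much less certain.

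**Conclusion.** The point holds, as a minor one. The collection list covers three of the four minor toxicities in the protocol's own rule, and nothing else in the supplied text commits to recording the fourth. If that list is followed as written, isolated light-headedness drops out of the side-effect comparison across saline, 0.1% and 0.2% ropivacaine.

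The size is unknown. The range of 0.4 to 4 women per arm rests entirely on assumed rates of 2% to 20%, and on the unseen form not already including the item. The primary outcome and the sample size are unaffected, and the clinical unblinding rule is not in question. This is a cheap improvement rather than an error.

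**What to change.** - Add light-headedness to the ropivacaine side-effect list in Objectives, unless the Data Collection Instrument already has it; in that case, align the Objectives wording with the form.
- Ask about it together with perioral numbness, metallic taste and tinnitus in all three arms, so that saline gives the background rate.
- Report it by arm in line with the Statistical Analysis section ("Categorical data will be reported as frequencies"), and show any rule-triggered unblindings and their reasons in the same table. Severe and allergic events from the abstracted records need only be included in that table.

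The cost is a line or two on the form. The downside is that some light-headedness unrelated to ropivacaine will be recorded, so the frequencies should be read as descriptive.
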